9.2.2.4 Tumor assessments during treatment period

Scans (CT or MRI with contrast unless contraindicated) for tumor assessments according to RECIST v1.1 and iRECIST are to be done every 14 weeks (\pm 14 days) until radiological disease progression or end of the study. A minimum of at least 9 weeks from start of treatment is mandatory for the 1st "on treatment" tumor assessment.

See Section 9.4 for further information on tumor assessments, and Appendix 16.2 for RECIST and iRECIST guidance.

9.2.2.5 End-of-treatment (EOT) visit

An end-of-treatment (EOT) visit will be performed within 14 days after permanent discontinuation of study treatment.

Note: If the study treatment was permanently discontinued after dose interruption/delay of more than 30 days, the active follow-up visit should also occur within 14 days of discontinuation. If the EOT and active follow-up visits will be scheduled at the same time, the visits can be combined.

23 MAY 2023 Version 6.0 Page: 106 of 181

The following examinations will be done:

- ECOG PS (see Section 9.6.3.6)
- Measure vital signs, including blood pressure, heart rate, respiratory rate and body temperature (see Section 9.6.3.5).
- Measure body weight. Additionally, BMI will be derived by the sponsor. See Section 9.6.3.3.
- Perform physical examinations (see Section 9.6.3.2) including cardiovascular, respiratory, and abdominal system, a complete review of body systems, neurological examination and assessment of skin status. Orientating tests of neurological function will be included.
- Collect blood for safety laboratory tests including clinical chemistry, hematology and coagulation panels (see Section 9.6.3.1).
 - o In patients with an elevated serum phosphate level ($\geq 7 \text{ mg/dL}$), phosphate levels should be evaluated weekly until resolution (serum phosphate < 7 mg/dL).
- Collect blood for hormone panel (thyroid function tests) (see Section 9.6.3.1). After primary completion, hormone panel (thyroid function test) should be done periodically, according to local standard of care.
- Blood sampling (pre-dose) for plasma-based biomarker analyses.
 - Note: the blood samples are intended for isolation of plasma to study tumor markers circulating in blood (see Section 9.7.1).
- Calculate eGFR according to MDRD abbreviated formula (see Appendix 16.4).
- Urine pregnancy test in women of childbearing potential (see Sections 9.6.2 and 9.6.3.1).
 - Note: Pregnancy test to be repeated as frequently as required by local regulations.
 A serum pregnancy test must be performed if the urine pregnancy test is positive.
- Optional 12-lead ECG (see Section 9.6.3.4) (at the investigator's discretion)
- Toxicity/AE assessment
 - Note: Chest X-ray should be done in case the patient shows symptoms of pulmonary toxicity.
- Ask patient for changes in vision and send patient for ophthalmological examination in case the patient reports any changes in vision (see Section 9.6.3.7)
 - o In case of any findings, see Section 9.6.3.7.
 - Note: Monthly ophthalmological monitoring of the treatment associated retinal abnormality is recommended to be continued until resolution of the abnormality and to be documented in the source data for patients whose treatment was permanently discontinued.
- Tumor assessment (CT or MRI) according to RECIST v1.1 and iRECIST (see Section 9.4) (within 14 days after permanent discontinuation of study treatment). This is not

23 MAY 2023 Version 6.0 Page: 107 of 181

necessary if the previous tumor evaluation was performed within 4 weeks (up to week 18) or within 7 weeks (beyond week 18).

- Review concomitant medications (see Section 8.1)
 - Note: from signing of PI/ICF for study treatment eligibility up to 30 days after the last administration of study treatment, all concomitant medications (including start/stop dates, dose, frequency, route of administration and indication) must be recorded in the patient's source documentation, as well as on the appropriate pages of the eCRF.
- Return of rogaratinib and diary.

9.2.3 Follow-up periods

After primary completion, follow-up information will not be collected after the safety assessment visit.

9.2.3.1 Active follow-up

After permanent treatment discontinuation, a safety assessment visit must be scheduled for all patients at least 30 (up to +7) days after the last dose of study treatment. If the study treatment was permanently discontinued after dose interruption/delay of more than 30 days, the active follow-up visit should occur within 14 days of discontinuation. If the EOT and active follow-up visits will be scheduled at the same time, the visits can be combined. In addition, any AEs after the active follow-up visit qualifying as SAEs or AESIs with an onset up to 90 days after last atezolizumab dosing that are reported to the sites need to be documented unless a new anti-cancer therapy has been initiated.

The following examinations will be done for all patients:

- Measure vital signs, including blood pressure, heart rate, respiratory rate and body temperature (see Section 9.6.3.5).
- Perform physical examinations (see Section 9.6.3.2) including cardiovascular, respiratory, and abdominal system, a complete review of body systems, neurological examination and assessment of skin status. Orientating tests of neurological function will be included.
- Collect blood for safety laboratory tests including clinical chemistry, hematology and coagulation panels (see Section 9.6.3.1).
 - o In patients with an elevated serum phosphate level ($\geq 7 \text{ mg/dL}$), phosphate levels should be evaluated weekly until resolution (serum phosphate < 7 mg/dL).
- Toxicity/AE assessment.
 - Note: Chest X-ray should be done in case the patient shows symptoms of pulmonary toxicity.

23 MAY 2023 Version 6.0 Page: 108 of 181

- Ask patient for changes in vision. If change in vision is reported, an ophthalmological examination must be performed (see Section 9.6.3.7).
- Review of concomitant medications (see Section 8.1)
 - Note: from signing of PI/ICF for study treatment eligibility up to 30 days after the last administration of study treatment, all concomitant medications (including start/stop dates, dose, frequency, route of administration and indication) must be recorded in the patient's source documentation, as well as on the appropriate pages of the eCRF.
- Document subsequent systemic anti-cancer therapy (if applicable)
- An optional tumor biopsy is highly encouraged to be taken during Cycle 2 or later and/or at the time of disease progression or recurrence as per investigator's decision, if technically feasible (see Section 9.7.1).

Additionally, up to primary completion, the following assessment is to be done for patients who discontinue study treatment for reasons other than radiological disease progression:

- Tumor assessment (CT or MRI) according to RECIST v1.1and iRECIST (see Section 9.4)
 - Note: During the active follow-up period, CT/MRI evaluations will be performed every 14 weeks ± 14 days (from the previous scan date) until disease progression and/or start of subsequent systemic anti-cancer treatment, whichever comes first, or any other criterion for withdrawal is met. No tumor assessments will be performed after primary completion.

9.2.3.2 Long-term follow-up

Long-term follow-up will not be performed after primary completion. All patients in the long-term follow-up period will be contacted (telephone contact by site is sufficient) every 3 months (±14 days) from completion of the active follow-up until the end of the study (i.e. until last patient's last visit [LPLV] (see Section 6.4.1.3)). If a patient is lost to follow-up, the site will try to contact the patient, the patient's relatives, or another doctor treating the patient, unless prohibited by local requirements. In addition, any AEs after the active follow-up visit qualifying as SAEs or AESIs with an onset up to 90 days after last atezolizumab dosing that are reported to the sites need to be documented unless a new anti-cancer therapy has been initiated

The information to be recorded at these contacts:

- Survival status
- Document subsequent systemic anti-cancer therapy (if applicable)

23 MAY 2023 Version 6.0 Page: 109 of 181

9.3 Population characteristics

9.3.1 Demographic

The following demographic characteristics will be collected:

- Year of birth
- Age at Informed Consent
- Gender
- Race (as allowed by local regulation) and
- Ethnicity (as allowed by local regulation).

Routine procedures performed before informed consent can be used as screening data.

9.3.2 Medical history

Medical history findings (i.e. previous diagnoses, diseases or surgeries) meeting all criteria listed below will be collected as available to the investigator:

- Start before signing of the informed consent for study treatment eligibility.
- Considered relevant for the patient's study eligibility.

Detailed instructions on the differentiation between (i) medical history and (ii) adverse events can be found in Section 9.6.1.1.

9.3.3 Other baseline characteristics

Baseline study disease characteristics to be collected **for all enrolled patients** (i.e. all patients signing the PI/ICF for FGFR testing) during the FGFR testing period:

- Urothelial carcinoma diagnosis/classification including
 - o date of initial diagnosis
 - type of assessment
 - o date of the most recent progression / relapse
 - histology
 - location of primary cancer
 - TNM classification of urothelial carcinoma at study entry according to the AJCC 8th edition
 - o grading at initial diagnosis

Prior systemic anti-cancer medications have to be reviewed and must be fully documented in the source data.

23 MAY 2023 Version 6.0 Page: 110 of 181

Further baseline study disease characteristics to be collected **for all FGFR-positive patients** enrolled for screening:

- Prior systemic anti-cancer medication.
- Liver metastases (absence vs. presence) and
- Visceral metastases (liver, bone, lung) (absence vs. presence)
- Prior anti-cancer therapy for urothelial carcinoma
 - Any prior medications, significant non-drug therapies and diagnostic procedures for the study indication will be collected, including:
 - Medications (any prior systemic anti-cancer therapy)
 - Trade name of medication
 - Dose of medication
 - Start date and end date
 - Surgery
 - Date of surgery
 - Type of surgery
 - Radiotherapy
 - Regimen
 - Location
 - Intent
 - Start date and end date
 - Cumulative dose
 - Local therapy
 - Diagnostic procedures
 - o All **non-study-indication-related** medications taken within 4 weeks before start of study treatment will be documented, including:
 - Trade name of medication
 - Reason for medication (indication)
 - Dose of medication
 - Start date and end date or if continuing at patient's last visit.
- Review TNM classification (AJCC 8th edition)

23 MAY 2023 Version 6.0 Page: 111 of 181

- Karnofsky performance status (see Section 9.6.3.6)
- Alcohol and smoking habits/history

MSKCC categories and Bellmunt risk score

Prognostic factors have been identified for both first- and second-line treatment of patients with urothelial carcinoma. MSKCC established a prognostic model predicting overall survival in first-line urothelial carcinoma, which includes Karnofsky performance status (see Section 9.6.3.6) and visceral metastases as independent prognostic factors (35). For second-line the Bellmunt score defines ECOG performance status, hemoglobin level and liver metastases as main adverse prognostic factors for overall survival (36).

Bellmunt risk score will be derived by the sponsor based on the following parameters collected during screening assessments:

- Hemoglobin level $< 10 \text{ g/dL } vs. \ge 10 \text{ g/dL}$
- ECOG PS $0 \text{ vs.} \ge 1$
- Liver metastases absent vs. present

MSKCC categories will be derived by the sponsor based on the following parameters collected during screening assessments:

- Visceral metastases (liver, bone, lung) absent vs. present
- Karnofsky performance status $\geq 80\%$ vs < 80%

9.4 Efficacy

Patient survival will be followed up and tumor assessment will be performed using computed tomography (CT) or magnetic resonance imaging (MRI) (with contrast unless contraindicated) to determine the efficacy variables of this study: objective response rate (ORR), disease control rate (DCR), duration of response (DOR), best overall response (CR, PR, SD, Non CR/Non PD, PD), progression-free survival (PFS) and overall survival (OS).

For definitions and analyses of the efficacy variables, please refer to Section 10.3.3.

Radiological tumor assessment

Radiological tumor assessments will be performed locally by investigators. All scan should be interpreted by the same radiologist/investigator during the study, where at all possible.

Tumor response will be measured using CT or MRI scans (with contrast unless contraindicated) and evaluated using RECIST v1.1 (37) (see Appendix 16.2) to determine the secondary efficacy variables (objective response rate [ORR], disease control rate [DCR] and duration of response [DOR], best overall response (CR, PR, SD, Non CR/Non PD, PD), and

23 MAY 2023 Version 6.0 Page: 112 of 181

progression-free survival [PFS]). According to RECIST v1.1, confirmation of PR and CR is not required considering the nature of the study and the protocol requirements.

In addition, modified RECIST v1.1 for immune-based therapeutics (iRECIST) will be documented as exploratory variables and used as supportive evidence for the detection of pseudoprogression and the determination of progressive disease for treatment decision (see (38) and Appendix 16.2).

To facilitate an independent evaluation of outcome in this study, tumor assessment imaging data will be collected, image quality controlled and stored for a potential central review of tumor evaluation by independent readers prior to the final efficacy analysis. The decision to perform the central review will be based on the outcome of the local efficacy assessments. Treatment decisions with immune-based therapeutics require assessment of the clinical presentation of patients that can only be performed by the investigator; therefore, central review will not be used for treatment decisions. Details will be outlined in the Image Review Charter. Images for tumor assessment, de-identified with respect to patient identification related privacy data (except study related subject identification number) will be collected for all patients enrolled at baseline and at all post-baseline evaluations and will be submitted for collection and image quality control to facilitate a potential central review. Specific information on image handling, imaging guidelines, instructions for image acquisition and image evaluation procedures will be outlined in the Imaging Manual for the study sites.

The first radiological tumor evaluation will be conducted during clinical screening within 28 days before start of study treatment (see Section 9.1). Tumor assessments are to be done every 9 weeks (± 7 days) starting from Cycle 1 Day 1 until radiological disease progression or end of the study. A minimum of at least 9 weeks from start of treatment is mandatory for the 1st "on treatment" tumor assessment.

For patients who discontinue study treatment without radiological disease progression, follow-up tumor evaluations will be performed (by CT or MRI) until progression of malignancy and/or start of subsequent systemic anti-cancer treatment, whichever comes first, or any other criterion for withdrawal is met. During the active follow-up period, CT/MRI evaluations will be performed every 9 weeks (from the previous scan date). After 1 year of follow-up, CT scans may be scheduled approximately every 12 weeks. After primary completion, no tumor assessments will be done.

The radiological evaluation must include computed tomography (CT) or magnetic resonance imaging (MRI) of the chest, abdomen and pelvis with contrast media unless contraindicated. In case of contraindication to both, iodinated contrast agent for CT and gadolinium based contrast agent for MRI, evaluation should be performed with MRI (except chest region). Chest CT is strongly recommended and preferred versus chest MRI. MRI shall be performed instead of CT when local regulations do not permit the use of CT as requested per protocol schedule.

At investigator's discretion, CT or MRI scan should be repeated at any time if progressive disease is suspected.

A CT (with contrast if not contraindicated) or MRI scan of the brain must be done at screening to exclude CNS metastasis. An MRI scan of the brain is required to confirm or

23 MAY 2023 Version 6.0 Page: 113 of 181

refute the diagnosis of CNS metastasis at baseline in the event of an equivocal scan. Patients with definitely treated stable CNS metastases may be eligible for the Study (see also Sections 6.1 and 6.2; inclusion/exclusion criteria).

If a CT scan for tumor assessment is performed in a positron emission tomography (PET)/CT scanner, the CT acquisition must be consistent with the standard for a diagnostic CT scan, i.e. adequate radiation dose and i.v. contrast, if intended to be used for target lesion measurements.

Bone scans (Technetium-99m) should be performed at screening if clinically indicated. If bone metastases are present at screening and cannot be seen on CT or MRI scans, or if clinically indicated, TC-99m bone scans should be repeated when complete response is identified in target disease or when progression in bone is suspected. New lesions in PET or bone scan should be confirmed by CT or MRI.

All scans should be done with the identical modality (CT or MRI) and the identical technique (e.g., slice thickness, field of view) to those obtained at baseline.

If radiographic changes are believed by the investigator to be secondary to drug induced inflammation and not to tumor progression (e.g. in case of suspected pseudoprogression), the investigator may postpone a diagnosis of progressive disease (PD) until the next radiographic evaluation in the study if all the following criteria are met:

- Evidence of clinical benefit (defined as the stabilization or improvement of diseaserelated symptoms) as assessed by the investigator.
- Absence of symptoms and signs indicating unequivocal progression of disease (including worsening of laboratory values [e.g. new or worsening hypercalcemia]).
- No decline in ECOG performance status that can be attributed to disease progression.
- Absence of tumor progression at critical anatomical sites (e.g. leptomeningeal disease) that cannot be managed by protocol-allowed medical interventions.

Treatment beyond initial RECIST v1.1-defined progression is permitted only for patients who are clinically stable to continue on treatment until next imaging assessment (\geq 4 weeks later); this next imaging assessment should be no longer than 8 weeks later, to ensure that patients remain fit for salvage therapies. A longer time frame before the next assessment might be reasonable if no effective salvage therapies are available.

In addition, treatment beyond progression should not delay an imminent intervention to prevent serious complications of disease progression (e.g. central nervous system [CNS] metastases).

Patients for whom radiographic disease progression is confirmed at a subsequent tumor assessment may be considered for continuing study treatment at the discretion of the investigator if they still meet the criteria above and in absence of unacceptable toxicity.

23 MAY 2023 Version 6.0 Page: 114 of 181

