Tumor assessments will be performed using computed tomography (CT) or magnetic resonance imaging (MRI) (with contrast unless contraindicated), and patient survival will be followed up to determine the efficacy variables of this study: objective response rate (ORR), disease control rate (DCR), duration of response (DOR), best overall response (CR, PR, SD, Non CR/Non PD, PD), progression-free survival (PFS) and overall survival (OS). Tumor response will be evaluated using the RECIST v1.1. In addition, modified RECIST v1.1 for immune-based therapeutics (iRECIST) will be documented and used as supportive evidence for the detection of pseudoprogression and the determination of progressive disease for treatment decision.

Tumor scans will be performed at screening (baseline), and then every 9 weeks (±7 days) starting from Cycle 1 Day 1 until radiological disease progression or end of the study. After primary completion, scans will be performed every 14 weeks (±14 days). A minimum of at least 9 weeks from start of treatment is mandatory for the 1st "on treatment" tumor assessment. If the investigator considers radiographic changes secondary to drug-induced inflammation and not to tumor progression, the investigator may postpone a diagnosis of progressive disease until the next radiographic evaluation in the study. Radiological tumor assessments will be performed locally by investigators. To facilitate an independent evaluation of outcome in this study, tumor assessment imaging data will be collected, image quality controlled and stored for a potential central review of tumor evaluation by independent readers. The decision to perform the central review will be based on the outcome of the local efficacy assessments. Central review will not be used for treatment decisions.

Up to primary completion, patients who discontinue the study treatment for any reason other than radiological PD will be followed for progression during active follow-up (which includes the safety follow-up period) until confirmed PD for this patient is observed.

Patient reported outcome (PRO)

Patient reported outcomes will be assessed using EORTC QLQ-C30 (at screening, on Day 1 of every cycle, at the EOT, and at the safety assessment visit of the active follow-up). After primary completion, PROs will not be required.

Type of control

Not applicable

23 MAY 2023	Version 6.0	Page: 11 of 181
Data Monitoring Committee	No	

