- I: For monitoring purposes of atezolizumab, blood (plasma) samples will be collected at the following time points: at Cycle 1 Day 1: pre-dose, 1 (EOI), 4 and 8

Integrated Clinical Study Protocol No. BAY 1163877 / 19131 Part A

23 MAY 2023 Version 6.0 Page: 92 of 181

Table 9–2: Schedule of evaluations: Treatment and follow-up periods

hours post-dose; and at Cycle 1 Day 15: approximately 336 hours post-dose.

- m: From signing of PI/ICF for study treatment eligibility up to 30 days after the last administration of study treatment, all concomitant medications (including start/stop dates, dose, frequency, route of administration and indication) must be recorded in the patient's source documentation, as well as on the appropriate pages of the eCRF.
- n: To have complete control over the distribution and use of the study drug, the drug accountability must be performed before new medication is handed out to the patient. Return of rogaratinib and diary at EOT visit.
- o: Patients will receive their initial single-dose of 800 mg rogaratinib in the morning of Cycle 1 Day 1, followed by serial PK blood sampling for 8 hours and a second dose of 800 mg rogaratinib in the evening. Rogaratinib will be administered continuously twice daily on all 21 days in each cycle. Oral administration of the morning dose of rogaratinib on Cycle 1, Days 1, 2, 8 and 15, and on Day 1 of subsequent cycles will be done with a member of the site.
- p: The radiological evaluation must include computed tomography (CT) or magnetic resonance imaging (MRI) of the chest, abdomen and pelvis with contrast media. Tumor assessments (CT or MRI) are to be done every 9 weeks (± 7 days) starting from Cycle 1 Day 1 until confirmed radiological disease progression or end of the study. After primary completion, scans will be performed every 14 weeks (±14 days). A minimum of at least 9 weeks from start of treatment is mandatory for the 1st "on treatment" tumor assessment. Formal efficacy assessment will be done according to RECIST v1.1. iRECIST will be assessed as exploratory endpoint.
- q: Radiological tumor evaluation (within 14 days after permanent discontinuation of study treatment). This is not necessary if the previous tumor evaluation was performed within 4 weeks (up to week 18) or within 7 weeks (beyond week 18).

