Until radiographic disease progression based on RECIST 1.1, there is no distinct iRECIST assessment.

Assessment and Decision at RECIST 1.1 Progression

For patients who show evidence of radiological PD by RECIST 1.1 the investigator will decide whether to continue a patient on study treatment until repeat imaging is obtained (using iRECIST for patient management). This decision by the investigator should be based on the patient's overall clinical condition and agreement.

Clinical stability is defined as the following:

- Absence of symptoms and signs indicating clinically significant progression of disease
- No decline in ECOG performance status
- No requirements for intensified management, including increased analgesia, radiation, or other palliative care

For any patient deemed **clinically unstable** the investigator should discontinue the study treatment.

If the investigator decides to continue treatment, the patient may continue to receive study treatment and the tumor assessment should be repeated 4 to 8 weeks later to confirm or reject PD by iRECIST and to ensure that patients remain fit for salvage therapies.

Tumor flare may manifest as any factor causing radiographic progression per RECIST 1.1, including:

- Increase in the sum of diameters of target lesion(s) identified at baseline to ≥20% and >5 mm from nadir
 - Note: the iRECIST publication uses the terminology "sum of measurements", but "sum of diameters" (SOD) will be used in this protocol, consistent with the original RECIST 1.1 terminology.
- Unequivocal progression of non-target lesion(s) identified at baseline
- Development of new lesion(s)

iRECIST defines new response categories, including iUPD (unconfirmed progressive disease) and iCPD (confirmed progressive disease). For purposes of iRECIST assessment, the first visit showing progression according to RECIST 1.1 will be assigned a visit (overall) response of iUPD, regardless of which factors caused the progression.

At this visit, target and non-target lesions identified at baseline by RECIST 1.1 will be assessed as usual.

23 MAY 2023 Version 6.0 Page: 178 of 181

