6.2.3 Exploratory Efficacy Variables

Exploratory efficacy variables defined according to RECIST version 1.1 will include disease control rate (DCR), duration of response (DOR), progression-free survival (PFS) (according to both RECIST and iRECIST), time to progression (TPP), time to response (TTR), overall survival (OS) and follow-up time.

These variables are defined as below:

Follow-up time is defined as the time from the date of first study treatment until death or the date of last contact, if the subject is still alive at the time of analysis.

Disease control rate (DCR) is defined as the percentage of subjects whose overall best response was not progressive disease (i.e. CR, PR, SD or Non CR/Non PD). Tumor assessments with SD as response, that is performed prematurely after assignment to treatment of the subject (i.e. substantially earlier than the first planned radiological tumor assessment at 9 weeks), will not be taken into account.

Duration of response (DOR) (for PR and CR) is defined as the time (days) from the first documented objective response of PR or CR, whichever is noted earlier, to disease progression or death (if death occurs before progression is documented). DOR will be defined for responders only, i.e. subjects with a CR or PR. The actual dates the tumor scans were performed will be used for this calculation. DOR for subjects who have not progressed or died at the time of analysis will be censored at the date of their last tumor assessment.

Kaplan-Meier (KM) product-limit estimates for median, 25th and 75th percentile with its 95% CI together with total number of subjects, total censored and total events will be provided for DOR per dose group. In addition KM survival curves will be presented for each dose group.

Progression-free survival (PFS) is defined as the time (days) from start of study treatment to date of first observed disease progression (investigator's radiological or clinical assessment) or death due to any cause, if death occurs before progression is documented. The actual date that the tumor scan was performed will be used for this calculation. If a tumor assessment is performed over more than one day (e.g. scans for chest and abdomen done on different days for the same evaluation), the earliest date will be used for the calculation of PFS. For subjects without documented radiological or clinical progression or death at the time of analysis, PFS will be censored at the last actual visit date of tumor evaluation.

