Kaplan-Meier (KM) product-limit estimates for median, 25th and 75th percentile with its 95% CI together with total number of subjects, total censored and total events will be provided for PFS per dose group. In addition KM survival curves will be presented for each dose group.

Overall survival (OS) is defined as the time (days) from start of study treatment to death due to any cause. Subjects alive at the date of data cut-off for analysis will be censored at the last date known to be alive. If a subject is lost to follow-up before any assessment after assignment to treatment, this subject will be censored at day 1.

KM product-limit estimates for median, 25th and 75th percentile with its 95% CI together with total number of subjects, total censored and total events will be provided for OS per dose group. In addition KM survival curves will be presented for each dose group.

Time to progression (TTP) is defined as the time (days) from start of study treatment to date of first observed disease progression (radiological or clinical). TTP for subjects without disease progression at the time of analysis will be censored at the last date of tumor evaluation. TTP for subjects who have no tumor assessments after baseline will be censored at day 1.

KM product-limit estimates for median, 25th and 75th percentile with its 95% CI together with total number of subjects, total censored and total events will be provided for TTP. In addition KM survival curves will be presented for each dose group.

Time to Response (TTR) is defined as the time (days) from start of study treatment to the date of first observed partial or complete response. Only subjects with a partial or complete response are considered for TTR.

KM product-limit estimates for median, 25th and 75th percentile with its 95% CI together with total number of subjects, total censored and total events will be provided for TTR. In addition KM survival curves will be presented for each dose group.

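### Section 9.4 and the synopsis let the investigator postpone the PD diagnosis itself, which contradicts Appendix 16.2 and leaves the RECIST 1.1 progression date undefined

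*Protocol*

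**What the plan says.** Protocol Section 9.4 deals with scans whose changes the investigator believes to be inflammatory. In that case "the investigator may postpone a diagnosis of progressive disease (PD) until the next radiographic evaluation in the study". Four conditions apply: symptomatic benefit, no clinical or laboratory sign of unequivocal progression, no ECOG decline due to the disease, and no progression at a critical site. The synopsis (Methodology, Efficacy) gives the permission without conditions: "the investigator may postpone a diagnosis of progressive disease until the next radiographic evaluation in the study".

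Other text treats RECIST 1.1 progression as a separate event:

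- Table 9-2, footnote p: "Formal efficacy assessment will be done according to RECIST v1.1. iRECIST will be assessed as exploratory endpoint".
- Appendix 16.2 defines PD by lesion measurements, new lesions or unequivocal non-target growth. It starts a distinct iRECIST assessment only after RECIST 1.1 progression, when "the first visit showing progression according to RECIST 1.1 will be assigned a visit (overall) response of iUPD".
- SAP 6.2.3 plans PFS by both RECIST and iRECIST under one definition, which "is defined as the time (days) from start of study treatment to date of first observed disease progression"; deaths also count, and the investigator may call progression on imaging or on clinical grounds. For the other progression endpoint, "Time to progression (TTP) is defined as the time (days) from start of study treatment to date of first observed disease progression".

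Assessment is local. Central review is optional, and the decision to do it depends on the local results (Section 9.4).

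**The concern.** PD is the category on which PFS, TTP, DOR and DCR turn. Permission to postpone the diagnosis is therefore different from permission to keep treating. Section 6.4.1.3 already allows treatment after RECIST 1.1 progression on the same four conditions, and Section 7.4.4 allows it in shorter form, so care does not depend on postponing the label.

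Two sites reading identical scans could record different histories: one PD and iUPD at the first qualifying scan, the other no PD until later or not at all. Because iUPD is triggered by RECIST 1.1 PD, a postponed PD also delays iUPD and blurs the RECIST-versus-iRECIST contrast in PFS. The choice rests on investigator judgement in an open-label, single-arm study. Its results will be read against figures such as the 23% ORR and 2.7-month median PFS that Section 3.4 cites for first-line atezolizumab alone.

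**Working it through.** **1. Recording rule.** For a scan that meets RECIST 1.1 PD with suspected pseudoprogression:

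| Source | RECIST 1.1 entry | iRECIST entry |
|---|---|---|
| Appendix 16.2 | PD at this scan | iUPD at this scan |
| Section 9.4 and synopsis, read literally | PD not diagnosed; substitute entry not stated | no trigger yet |

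Neither document says whether a PD called later is dated back.

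**2. Direction if the postponed label or date is used.**

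- PFS and TTP: the recorded date is the same or later. If there is no later scan and the patient is alive, the event becomes a censoring at the same date. Both can only stay the same or lengthen.
- DCR: a PD as best response may become SD. The reverse cannot happen.
- ORR: best response runs to the end of treatment (Appendix 16.2), so a CR or PR after an unrecorded PD could count.
- DOR: it lengthens for a responder whose PD is postponed. Patients who respond only after an unrecorded PD also join the responder set, so the direction of the distribution is not fixed.

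**3. Length of one postponement.** Section 9.4 and Appendix 16.2 put the repeat scan at 4 to 8 weeks; the regular interval is 9 weeks. The reference median is 2.7 × 365.25/12/7 = 11.74 weeks.

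- 4 weeks: 4/11.74 = 34% of that median; a week-9 PD moves from day 63 to day 91.
- 8 weeks: 68%; day 63 to day 119.
- 9 weeks: 77%; day 63 to day 126.

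**4. Response scale.** The plan's own figure is in Section 10.4 (n=26, Jeffreys prior, posterior Beta(0.5+r, 26.5−r)):

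- r ≤ 7: P(π ≤ 0.4 | data) is at least 91.6%; P(X ≤ 7 | 0.15) = 96.8%. Stated: 91% and 96%.
- r ≥ 14: P(π > 0.4 | data) is at least 92.4%; P(X ≥ 14 | 0.6) = 80.1%. Stated: 92% and 80%.

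Both reproduce. One patient is 1/26 = 3.8 points of ORR or DCR. One extra responder, from 13 to 14, moves P(π > 0.4) from 85.1% to 92.4%. From 7 to 8 it moves P(π ≤ 0.4) from 91.6% to 83.1%.

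**5. Illustration only.** Assumptions, none from the documents: exponential event times, 15% of events are deaths, a share q = 10–30% of PDs is postponed, and a postponed week-9 PD is entered as SD.

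- P(event by week 9) = 1 − exp(−ln 2 × 9/11.74) = 0.412. Excluding deaths: 0.412 × 0.85 = 0.350.
- DCR gain = 0.350 × 0.10 to 0.350 × 0.30 = 3.5 to 10.5 points (0.9 to 2.7 of 26 patients), from about 59% to 62–69%.
- Simulated PFS with delays of 4 to 9 weeks: the mean rises by 0.3 to 2.3 weeks; the median stays at the 18-week scan.
- With an assumed underlying median of 26 weeks, median PFS stays at 27 weeks for q = 10%, and becomes about 31–32 weeks for q = 20% and 31–36 weeks for q = 30%.

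**The case against.** The strongest reply is that the documents, read together, keep the first RECIST 1.1 date. Directly after the four conditions, Section 9.4 speaks of treating beyond an initial RECIST 1.1-defined progression, as if PD were already established. Appendix 16.2 places RECIST 1.1 PD before any iRECIST label, and its SD definition excludes a scan that qualifies as PD. The SAP plans PFS under both criteria. The Imaging Manual, not available here, may settle the recording. This stands to the extent that any bias is conditional. A reader might infer that the endpoints are certainly a RECIST/iRECIST hybrid biased upward; the documents support an unresolved contradiction, not that certainty.

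Three further inferences also go too far:

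- That postponement doubles PFS (day 63 to 126). This needs the regular 9-week scan. Section 9.4 normally expects 4 to 8 weeks and accepts a longer gap when no effective salvage therapy is available.
- That DCR rises by a known amount. The postponed share is assumed. Clinical progressions and patients who fail the four conditions should not be postponed, so the illustration is on the high side.
- That DOR is inflated. Late responders can pull it either way.

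It is also fair that the primary objective is safety, nothing is tested, and Section 10.3.3 and SAP 6.2 make only ORR secondary (Section 9.4 words DCR, DOR and PFS as secondary too). The amendment log cites a July 2021 data cut, and Section 5.2.3 plans no further analysis after primary completion, so rewording Section 9.4 cannot change data already recorded. That weighs toward the SAP part of the fix. It does not supply the missing dating rule.

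**Conclusion.** The contradiction between Section 9.4 with the synopsis and Appendix 16.2 is real, and no recording or dating rule resolves it. If Section 9.4 is applied literally, PFS, TTP and DCR can move only in the favourable direction or not at all, and ORR is exposed through responses after an unrecorded PD. The sizes that rest on the documents are per patient: normally 4 to 8 weeks of PFS or TTP, and 3.8 points of DCR or ORR at n=26. The total effect is unknown because the number of postponements is unknown. In the illustration DCR is sensitive, while median PFS at the 2.7-month reference does not move for delays of 4 to 9 weeks.

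The consequence is limited to interpreting descriptive, single-arm results against published RECIST 1.1 figures. The point deserves correction because the remedy is cheap and leaves care as written.

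**What to change.** **Protocol (Section 9.4 and synopsis).** Reconcile both with Appendix 16.2 by stating that:

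- RECIST 1.1 PD is recorded and dated at the first scan meeting its criteria;
- only iRECIST confirmation and the treatment decision may be deferred, with treatment beyond progression left as Section 6.4.1.3 has it;
- no RECIST 1.1 response is counted after that date.

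**SAP (Section 6.2).** For existing data:

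- derive RECIST 1.1 PD from recorded target-lesion sums, new lesions and recorded non-target status;
- report the number of postponed PDs;
- show PFS, TTP, DCR and ORR by both the derived and the investigator-called date, so that neither is presented alone.

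**Cost.** A few sentences of protocol and eCRF guidance, one derivation, and one extra set of tables. PFS, DCR and ORR may look slightly less favourable. The derivation cannot recover unequivocal non-target progression that an investigator judged but withheld; the report should say so.
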